A growing body of literature spanning cognitive science, education, and more recently, psychiatry, has associated inaccurate judgements of performance, or poor Introspective Accuracy (IA), with poor functioning. We define IA as the discrepancy between objective data and subjective estimation of task performance, ability, or behavior^{5,22}. Our published work and that of others has identified the following: 1) Poor IA is Predictive of Poor Functioning: Poor IA, as measured by greater discrepancies between actual and judged performance, accounts for up to 42% of the variance in disability in social and nonsocial functional domains²³⁻²⁶; 2) IA is Independently Associated with Functioning Beyond Capacity: The contribution of IA to disability is independent from that associated with actual cognitive and social cognitive performance, and the relationship between cognition and functioning is minimal (~3% of variance)^{27,28} once IA is accounted for; 3) IA Impairments are Worse in Psychotic Disorders vs. Other Conditions: In contrast to bipolar disorder, people with psychotic disorders produce judgements that are not correlated with actual performance despite contemporaneous feedback²⁹, indicating substantial disruption in self-assessment processes; 4) IA Impairments are Conserved across Domains and

Measurement Modalities: Discrepancies between self-assessments and informant reports of functioning are associated with task-based IA deficits^{5,23}. In each of these studies, participant self-assessment was poorly linked to objective data even with performance feedback (e.g. task feedback³⁰; objective data regarding vocational outcomes^{28,31})

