3 OBJECTIVES AND ENDPOINTS

In this pilot project, there are two objectives. Firstly, we will evaluate, in an open trial, whether iTEST is acceptable, indexed by adherence, and engages IA as a target, indexed by improved IA on trained

tasks and transfer on an untrained task in a different domain. Secondly, we will evaluate optimal dosing of the intervention, by whether go/no-go criterion for improvement is achieved at 8, 12, or 16 weeks.

Our go/no go criteria are threefold: 1) To demonstrate feasibility, the average adherence must be equal to or exceed 75%, 2) To show target engagement, we require a significant improvement in IA ($d > .50$) on both trained tasks, and 3) To show transfer of training, we require significant improvement in IA ($d > .50$) on the untrained Wisconsin Card Sorting Task. Criteria may be met prior to 16 weeks, at weeks 8 or 12 (Note: all participants continue through 16 weeks).

OBJECTIVES	ENDPOINTS	JUSTIFICATION FOR ENDPOINTS
Primary		
To evaluate the acceptability and preliminary impact on our target, IA	
Adherence defined as the ratio of completed mobile prompts completed divided by the number possible – 75% is the criterion
 
Clinically significant (Cohen's $d > 0.5$) improvement in trained introspective accuracy as measured by IA on our Verbal Learning and Memory Test and Mobile Electronic Test of Emotion Recognition tasks. These are administered 6x per week for 16 weeks.
 
Clinically significant (Cohen's $d > 0.5$) improvement in untrained introspective accuracy (global resolution score) on the WCST. The WCST is administered at baseline, 8, 12 and 16 weeks.
	
Adherence at a level of 75% is generally accepted in mobile intervention studies such as this
 
The reason that trained tasks are part of our Go/No Go criteria is because lack of improvement on trained tasks would call into question the ability of iTEST to modify IA, and would indicate need for program revisions. IA is calculated as the discrepancy (absolute) between each trial's correct performance from that estimated by the participant, which is nested within sessions and weeks.
 
An additional Go/No Go component is transfer of training to an untrained task-based measure of IA, the Meta-Cognitive Wisconsin Card Sorting Test¹³. IA on this task is also associated with functioning and improvement on this task would support that iTEST

OBJECTIVES	ENDPOINTS	JUSTIFICATION FOR ENDPOINTS
		leads to generalized improvement in IA.
Secondary		

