trained; (4) In the final stage, response options are expanded to include a level of certainty rating, and these responses are connected to scoring to incentivize choice for high- and low-confident responses across levels of difficulty. Feedback is provided in the form of discrepancy and its direction (i.e., “*you guessed a number correct that was 3 words higher than what you actually got correct*”) which is translated to a score that is displayed in a “leaderboard” displaying progress during training. At the end of each session, questions ask what strategies the participant used to estimate their performance and what strategies could improve their score, with responses collaboratively developed with the Coach during coaching.

To deliver iTEST, we will use the NeuroUX platform, <https://www.getneuroux.com/>, a HIPAA compliant platform, for administration of iTEST. Information Technology infrastructure will securely collect the data gathered by smartphones and will store the information via transfer to an encrypted Amazon Web Service (AWS) server. AWS offers a simple and intuitive web-based user interface from user to server. It is an easy-to-use cloud computing platform that allows various storage services for backup, archiving, and disaster recovery use cases. AWS enables robust safeguards to help protect the privacy of the data with highly secure AWS Data centers. Specifically within AWS, data will be stored in the Amazon S3 service and will be used for large-scale analytics. Amazon S3 provides scalable and durable object storage in the cloud. S3 is where the experimenters will be storing the user information (phone number, start and end time) along with the survey links. Once the data is generated, the data will be stored securely in this server, which will only be accessible by study staff. The transmitted program elements are encrypted and separated from any identifiable information. No information is stored locally on the smartphone device and cannot be accessed by anyone if the device will be lost or stolen. The developer wrote a whitepaper for Institutional Review Boards that gives an executive summary of Amazon Web Service’s security: <https://aws.amazon.com/whitepapers/>.

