8.2 SAFETY AND OTHER ASSESSMENTS

Baseline Assessment: At the baseline assessment, we will collect demographic and social contextual information (e.g., living situation) and we will gather medication data including sedation/sleepiness side effects via the Karolinska scale³⁴ at all assessment points. All participants will continue to receive their current treatments, as determined by their clinical providers throughout the study. We will also administer the Brief Assessment of Cognition in Schizophrenia-App Version (BACS)³⁵ and Virtual Reality Functional Capacity Assessment Tool³⁶ (VRFCAT) to assess global cognition and functional capacity, respectively, at baseline^{37,38}. In some past mobile interventions (with no coaching) adherence was poorer in patients with lower cognitive ability³⁹, so we will explore neurocognitive ability as a moderator. iTEST is designed to accommodate cognitive impairment by including device/app practice, a simplified guided user interface, and bi-weekly coaching. Finally, we will administer the Treatment Rationale Scale⁴⁰ to evaluate expectancies. Participants will receive 20 dollars for completing the screening portion of the baseline assessment and additional 30 dollars for completing the second part of the visit if eligible for a total of 50 dollars.

Symptom Assessments: Depression and psychotic symptoms will be assessed with the Calgary Depression Scale for Schizophrenia (CDSS)⁴¹ and Positive and Negative Syndrome Scale (PANSS)²⁶.

Table 3. Measures, Constructs, and Indicators		
Construct	Measure	Operational Indicator
Sample Characterization/Exploratory Moderators		
Cognition	BACS (Baseline only)	Total Score
Functional Capacity	VRFCAT (Baseline only)	Total Score
Psychotic Symptoms	PANSS Positive and Negative	Total Score
Depressive Symptoms	Calgary Depression Scale (CDSS)	Total Score
Treatment Expectancies	Treatment Rationale Scale	Total Score
Trained Task-Based IA Target (R61,R33)		
Trained Task-based IA	IA on METER and VLMT	Estimated vs Actual correct
Transfer of Training Target (R61, R33)		
Untrained Task-based IA	Metacognitive WCST	Global resolution score
Primary Outcome (R33; Exploratory in R61)		
Functional Outcome	Informant-Rated SLOF	Total Score
Secondary Outcomes		
Life space Mobility	GPS	Daily distance from home
Exploratory Mechanisms		
Strategy Use; Motivation and Defeatist Beliefs	Compensatory Cognitive Strategies Scale; CAINS Motivation, Defeatist Performance Beliefs	Total scores

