9 STATISTICAL CONSIDERATIONS

9.1 STATISTICAL HYPOTHESES

The statistical hypotheses are that adherence will exceed the criterion of 75% and that there will be a pre-post change in the VLMT, METER and WCST tasks that will exceed that of 0.5 Cohen’s d with the baseline sample wide standard deviation serving as the denominator.

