As shown in Figure 1, at Level 1 (trials within weeks), participants' judgments of their performance on a task at trial t on week w will be regressed on their objective performance on that same task at trial t on week w (e.g., participants' judgments of their performance on trial t of the list-learning/METER task at week w will be regressed on their objective performance on trial t of that same list-learning task at week w). In line with the Truth and Bias model framework⁵⁴ participants' judgments of their performance will be centered on the grand-mean for objectively assessed performance, and their scores for objective performance will be centered on the mean for their objective performance that week. This centering strategy renders the intercept for participants' judgments of their performance to be the average trial-to-trial difference between their judgment of their performance and the grand-mean for objective performance at week w (e.g., IB for list learning/METER at week w ; see IB-LL/FE in Figure 1). Moreover, the slope for this regression captures participants' capacity to accurately track the lows and highs of their performance across the trials for that week (e.g., IA for list learning/METER at week w ; see IA-LL/FE in Figure 1). To estimate systematic change in IA across the trials (see, e.g., Change in IA-LL/FE in Figure 1), we will regress participants' judgments of their performance at trial t on week w (which is technically IA given the centering strategy) on trial number (grand-mean centered).

The black dots placed on parameters at Level 1 in Figure 1 indicate the estimation of random effects to permit for the heterogeneity of those Level 1 effects across the weeks in the study for participants. Thus, at Level 2 (weeks within persons), we will estimate week-to-week differences in participants' average

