levels of IB across the trials, participants' levels of IA, and participants' average changes in IB across the trials (see, e.g., the circles for IB-LL/FE at week w , IA-L/FE at week w , and Change in IB-LL/FE at week w in Figure 1, respectively). Further, to estimate systematic change in IA across the weeks (see, e.g., Change in IA-LL/FE in Figure 1), we will regress participants' IA at week w on week number (grand-mean centered). Because IA is operationalized as a slope (as opposed to a mean-level difference like IB), we estimate change in IA at Level 2 so that reliable estimates of IA can be obtained each week (e.g., 18 trials contribute to IA for list learning). Although not depicted in Figure 1, we will include additional Truth and Bias models at Level 2 for WCST targets of transfer wherein participants' judgments of their abilities assessed at week w are regressed on their objective performance for that domain at week w (e.g., participants' judgments of how many WCST items they got correct at week w will be regressed on their objective performance on the WCST at week w). We will use the same centering strategy described previously to render the intercepts and slopes from the regressions as indices of IB and IA, respectively.

The black dots placed on parameters at Level 2 in Figure 1 indicate the estimation of random effects to permit for the heterogeneity of those Level 2 effects across participants in the study. Thus, at Level 3 (persons), we will estimate individual differences in participants' average levels of introspective bias across the trials and weeks, participants' average levels of introspective accuracy across the weeks, participants' average changes in introspective bias across the trials and weeks, and participants' average changes in introspective accuracy across the weeks (see, e.g., the circles for Mean IB-LL/FE, Mean IA-LL/FE, Mean Change in IB-LL/FE, and Change in IA-LL/FE in Figure 1, respectively). We will evaluate R61 Aim 1 by inspecting the standardized mean-level differences for Change in IA-LL/FE in Figure 1 at weeks 8, 12, and 16. Similarly, we will evaluate R61 transfer of training by inspecting the standardized mean-level differences for changes in IB and/or IA for the WCST.

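### Go criterion 2 is defined on an absolute judged-versus-actual discrepancy, but Section 9.4.1 decides it on a regression slope that a constant over-estimate leaves unchanged

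*Combined protocol and SAP*

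**What the plan says.** **The endpoint.** Section 2.2 gives the general definition: "We define IA as the discrepancy between objective data and subjective estimation of task performance, ability, or behavior". For the trained tasks, Section 3 is specific: "IA is calculated as the discrepancy (absolute) between each" trial's number correct and the participant's own estimate of it. Section 8.1 repeats this, and Table 3 in Section 8.2 lists the indicator as "Estimated vs Actual correct". The go rule in Section 3 is that "we require a significant improvement in IA ($d > .50$) on both trained tasks". Section 9.1 sets the scale of d, "with the baseline sample wide standard deviation serving as the denominator".

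**The analysis.** Section 9.4.2 refers the primary analysis to Section 9.4.1, which also says that there is no formal SAP. There, judgments are regressed at Level 1 on performance centred at that week's mean. The slope is named IA and the intercept IB. The text later confirms the choice: "Because IA is operationalized as a slope (as opposed to a mean-level difference like IB". Aim 1 is then evaluated on the standardized change in IA for list learning and emotion recognition at weeks 8, 12 and 16. For the WCST, by contrast, the text allows a change in IB, in IA or in both.

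**The training.** Section 6.1.1 says "Feedback is provided in the form of discrepancy and its direction".

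**The concern.** One name covers two quantities. The endpoint sections score how far a judgment lies from the truth. The analysis section scores how well judgments rise and fall with performance. No section says how the discrepancy score is to be analysed, or how a change in slope translates into a change in discrepancy.

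Their directions differ as well. A smaller discrepancy is better, while a slope is better the nearer it is to 1. Section 9.2 quotes power for a change in IA of both d = −0.50 and d = 0.50 without naming the score.

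Criterion 2 helps decide whether the randomized R33 trial proceeds (Section 1.2), and the earliest time point that meets the criteria sets its dose (Sections 4.1 and 9.4.3). If the two scores disagree, the plan as written gives an answer about a quantity other than the one it defined.

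**Working it through.** **1. The plan's own figure.** Section 9.2 states power of .91 (n = 48, 8 weeks) to .97 (n = 60, 16 weeks) for |d| = 0.50. The three-level simulation cannot be rerun, because its variance components and alpha are not given. A paired-change t approximation (two-sided .05 assumed) has noncentrality 0.5·√n, which is 3.46 at n = 48 and 3.87 at n = 60. Power is .924 and .968, close to the stated values. With d in baseline-SD units, the standardized change is d/√(2(1−r)), where r is the pre-post correlation. At r = .5 this is again 0.5, with the same power. At r = .3 it is 0.423 (power .82 and .90), and at r = .7 it is 0.645 (.99 and 1.00). The power figures therefore do not show which score or which SD was meant.

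**2. The slope under a constant shift.** With performance p and judgment J, the slope is Σ(p − p̄)(J − J̄) / Σ(p − p̄)². Adding c to every J also adds c to J̄, so the slope does not change. In one simulated week of 18 trials (the number per week in Section 9.2):

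| Items added to every judgment | Slope | Mean absolute discrepancy |
|---|---|---|
| 0 | 0.588746 | 1.53 |
| 1 | 0.588746 | 2.47 |
| 3 | 0.588746 | 4.47 |
| 5 | 0.588746 | 6.47 |

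A participant who always judges 3 too high (J = p + 3) has slope 1 and discrepancy 3. After full correction (J = p) the slope is still 1 and the discrepancy is 0. This step needs no assumption about SDs.

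**3. Whether IB fills the gap.** Under the plan, "judgments of their performance will be centered on the grand-mean for objectively assessed performance", while performance is centred on the person's own weekly mean. The intercept is then mean judgment minus grand-mean performance. With perfect self-judgment (J = p) it equals the person's weekly mean minus the grand mean, which moves whenever performance moves. It is also signed. It is not the absolute discrepancy, and it is not named in the trained-task rule.

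**4. Labels.** Section 9.4.1 attaches Change in IA-LL/FE first to a regression of judgments on trial number, then to a regression of the weekly slope on week number. It later describes the trial-level change as change in IB.

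**5. Size (illustration only).** The documents give no SDs, list lengths or mean scores. Assumed: n = 60, 18 trials a week, mean over-estimate 2.5 items (SD 1.5), slope 0.5 (SD 0.25), within-person performance SD 2, judgment noise SD 1.5, 400 replicates. Positive d means improvement.

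| Headroom above mean performance | Slope d, 60% of over-estimate removed | Slope d, slope up 0.2 and bias up 0.5 item | Discrepancy d, same case as previous column |
|---|---|---|---|
| No ceiling | 0.00 | about 0.64 | −0.28 |
| 6 items | 0.11 | – | – |
| 4 items | 0.39 | 0.36 | −0.13 |
| 2 items | 0.65 | 0.19 | 0.03 |

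In the first case the discrepancy d is about 0.94 with no ceiling, and on rerunning it stayed above 0.5 at each of the three ceilings. The two scores thus disagree about 0.5 with no ceiling and at 6 and 4 items, and agree at 2. In the second case a go on the slope alongside a worse discrepancy appears with no ceiling and is gone at 4 items.

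A second uncapped set of assumptions (over-estimate 3 items, between-person SD of bias 0.5 to 2.0, other values as above, 20,000 persons) shows the same pattern. Over-estimation falling from 3 to 0 improves the discrepancy by d = 0.76 to 2.83 with slope d about 0. Raising the slope by half an SD with bias fixed improves the discrepancy by only 0.03 to 0.05.

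**The case against.** The best defence has four parts.

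- *Bounded tasks.* Judgments count words or faces, so the list length caps them. Over-estimation pressed against a ceiling flattens the slope, and removing it then raises the slope. This stands: a reader might infer that the slope is blind to over-estimation in practice, or that 0.94 against 0.00 is typical. Neither follows, because the documents give no list lengths or mean scores. The no-ceiling figures are an extreme.
- *What is trained.* Section 6.1.1 also trains the use of trial-by-trial feedback and the matching of confidence to difficulty. A slope does measure tracking. So it misses part of what is trained, not all of it. Size and direction of error are nevertheless fed back, and one stage advances on a discrepancy within ±1.
- *The model estimates IB.* True, but for the trained tasks Section 9.4.1 puts only the change in IA into the decision. Section 2.2 reports no practice effects from repeated testing alone, so how far IB would drift with performance is unknown.
- *Which parameter decides.* The duplicated label leaves some doubt, and Figure 1, which carries the labels, is missing from the text available here. But the explicit statement that IA is a slope governs the week-level change, and neither labelled regression has the absolute discrepancy as its outcome.

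A reader might also infer that the denominator of d shifts between sections, or that the Section 9.2 power holds only in units of the SD of change. The documents do not support this. Section 9.1 states the baseline SD, Section 9.4.1 names no other, and step 1 shows that baseline-SD units at an assumed r = .5 give the same power.

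**Conclusion.** The conflict is real, and it is an error in the plan as written rather than a missing detail. Sections 3 and 8.1 define one quantity, Section 9.4.1 decides on another, and nothing links them. That a slope does not move under a constant shift is algebra.

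How often the go decision would actually differ cannot be determined from the documents. It depends on the spread of bias and of slopes, and on the distance between typical scores and the list-length ceiling. Under the assumptions shown, the disagreement runs from a clear pass on the discrepancy with no change in slope (ample headroom) to agreement on the 0.5 threshold (about 2 items of headroom). On denominators, the most that can be asked is for Section 9.4.1 to say that its standardized change uses the Section 9.1 baseline SD.

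**What to change.** In Section 9.4.1:

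- Make the Level 1 outcome for go criterion 2 the absolute judged-minus-actual discrepancy per trial, as defined in Sections 3 and 8.1, and state that lower is better.
- Estimate the change from baseline to weeks 8, 12 and 16 for each task, and divide it by the observed baseline SD of that score, as Section 9.1 specifies.
- Because list length varies, either adjust for it or report the discrepancy as a share of list length as a sensitivity analysis. Items remain the natural primary unit, since Section 6.1.1 sets progression in items.
- Keep the Truth and Bias slope and IB as supportive results. They show whether a change comes from less bias or from better tracking, which the discrepancy alone cannot separate.
- Use the label for change in IA for one parameter only.

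In Section 9.2, state which score, direction and SD the power refers to.

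The cost is a modest re-specification, and a new power run if the existing one was built on the slope. An absolute discrepancy cannot be negative and may be skewed, so the model should allow for that. No new data are needed: judged and actual counts are already recorded on every trial, and Section 6.1.1 already provides mobile assessments at baseline.

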9.4.2 ANALYSIS OF THE PRIMARY EFFICACY ENDPOINT(S)

These are detailed in 9.4.1

9.4.3 ANALYSIS OF THE SECONDARY ENDPOINT(S)

To evaluate the briefest dose of the intervention, we will inspect changes at weeks 8, 12, and 16. We will evaluate which of these time points reaches the criterion (Cohen's $d=0.5$) for our primary endpoints.

We will also evaluate whether change in the Specific Level of Functioning (SLOF) scale exceeds $d=0.5$ improvement. Analyses will follow the same approach as in 9.4.1, employing linear mixed models in the intent to treat sample.

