4.1 OVERALL DESIGN

Hypothesis:

Target Engagement Hypothesis: Participants' adherence and average changes in IA for the mobile tasks and pre- post differences in meta-cognitive WCST will meet or exceed our go/no go criteria

Optimal Dosing: Target engagement may occur prior to 16 weeks, at week 8 or 12. We would select the optimal dose for the R33 is determined by selecting the earliest assessment point that reaches go/no go criteria - all participants receive the same dose

Phase of the trial, if applicable: This is a pilot behavioral intervention and so study phases are somewhat difficult to apply but would be mostly consistent with a Phase Ib study that is investigating acceptability and a preliminary effect in a diseased population

Design of Trial: Single arm, unblinded, open pilot trial.

Methods used to minimize bias: Measures are standardized and accepted endpoints and the sample has few exclusion criteria for entry

Dosing: All participants receive the same dose. We will investigate the point at which (among 8, 12, and 16 weeks) go/go criteria are met.

Intervention groups: This is a single arm trial and the duration of the intervention is 16 weeks.

Sites: There will be 2 sites – UCSD is the prime site and University of Texas at Dallas will be the secondary site with their own IRB.

Study Intervention: iTEST

Interim Analysis: No interim analysis is planned

Stratification: None

Name of sub-studies, if any, included in this protocol: None

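### Section 9.4.3 selects the duration on Cohen's d alone while Section 4.1 uses the full go/no-go criteria, and adherence has no usable definition at weeks 8 and 12

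*Combined protocol and SAP*

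**What the plan says.** All references are to the combined protocol and SAP.

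- **Section 3** sets three go/no-go criteria. The first is "To demonstrate feasibility, the average adherence must be equal to or exceed 75" percent. The second ("To show target engagement, we require a significant improvement in IA") asks for d above 0.50 on both trained tasks. The third ("To show transfer of training, we require significant improvement in IA") asks for the same on the WCST. On timing it adds: "Criteria may be met prior to 16 weeks, at weeks 8 or 12".
- **Section 3** also describes the dosing objective more narrowly, as judged "by whether go/no-go criterion for improvement is achieved at 8, 12, or 16 weeks".
- **Section 4.1** counts adherence among the quantities expected to meet the go/no-go criteria. It chooses the R33 dose by "selecting the earliest assessment point that reaches go/no go criteria". The synopsis (Section 1.1) likewise links the briefest duration to criteria in the plural.
- **Section 6.4** defines adherence as completed training sessions over the number possible, and gives that number as 6 per week for 16 weeks, or 96.
- **Section 9.1** restates the 75% adherence hypothesis.
- **Section 9.4.1** describes the multilevel models for introspective accuracy and bias, and says there is no formal SAP. **Section 9.4.2** says only "These are detailed in 9.4.1". **Section 9.4.3** takes weeks 8, 12 and 16 and says "We will evaluate which of these time points reaches the criterion", giving Cohen's d = 0.5 as that criterion. Adherence is not mentioned anywhere in 9.4.

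**The concern.** The choice of duration is what Aim 2 delivers, and the document gives two rules for it. Under Section 4.1 a time point qualifies only if it meets the go/no-go criteria, adherence included. Under Section 9.4.3 it qualifies on effect size alone. The two rules agree only while adherence is comfortably above the threshold.

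Adherence is also left without the pieces that the Section 4.1 rule needs. No estimate is planned at weeks 8 or 12, and the one numerical denominator covers the full 16 weeks. Someone applying the go/no-go criteria at an earlier point would have to choose a denominator at that stage, possibly with the data in view.

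The two outcomes can separate in practice. Section 7.1 keeps participants in the study after they stop iTEST. Section 6.1.1 lets them continue paid assessments without training, and it schedules mobile assessments separately from training. Effect sizes can therefore be estimated when training completion is low.

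**Working it through.** **1. The plan's own figure.** Section 6.4: 6 sessions per week × 16 weeks = 96, which reproduces. The 75% threshold is 0.75 × 96 = 72 sessions.

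**2. That denominator at each assessment point.** Scheduled sessions to week w are 6 × w.

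| Week | Scheduled to date | Highest possible adherence over 96 | 75% of sessions scheduled to date |
|---|---|---|---|
| 8 | 48 | 48/96 = 50% | 36 |
| 12 | 72 | 72/96 = 75% | 54 |
| 16 | 96 | 96/96 = 100% | 72 |

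Read literally, the adherence criterion can never be met at week 8. It can be met at week 12 only if no participant misses a session. Section 3 says the criteria may be met at either point.

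**3. Illustration of the two rules diverging.** Assumed mean completion, not from the documents: 80% in weeks 1-8, 65% in weeks 9-12, 55% in weeks 13-16.

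- Week 8: 48 × 0.80 = 38.4 sessions. 38.4/48 = 80%; over 96, 40%.
- Week 12: 38.4 + 24 × 0.65 = 54.0 sessions. 54.0/72 = 75%; over 96, 56.25%.
- Week 16: 54.0 + 24 × 0.55 = 67.2 sessions. 67.2/96 = 70%.

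Case A: the d criterion is first reached on VLMT, METER and WCST at week 16. Section 9.4.3 names 16 weeks. The go rule rejects it, because 70% is below 75%.

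Case B: the d criterion is reached on all three at week 8. Section 9.4.3 names 8 weeks. The go/no-go rule with the 96-session denominator rejects week 8 (40%), although adherence to that point was 80%.

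**4. How the adherence criterion behaves alone.** Assumptions: n = 60 (Sections 1.1 and 9.2), between-person SD of 20 to 30 points (not in the documents), normal approximation. P(observed mean < 75) = Φ((75 − μ)/(SD/√60)).

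- True mean 70%, SD 20: SE = 20/√60 = 2.58, z = 1.94, P = 0.974. SD 30: SE = 3.87, z = 1.29, P = 0.902. The observed mean therefore reaches 75% in about 3% to 10% of trials.
- True mean 75%: P = 0.50.
- True mean 80%: P = 0.026 to 0.098.
- True mean 85%: P at most 0.005.

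These probabilities concern the adherence criterion only. They do not include the chance that d reaches 0.5 on all three tasks.

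**The case against.** Four points can be made for the plan.

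*Section 3 partly supports Section 9.4.3.* Its dosing sentence speaks of a criterion for improvement, which fits a rule based on d alone. This stands. The inconsistency lies partly within Section 3, so a reader should not infer that 9.4.3 simply misstates an otherwise uniform design.

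*The overall gate still contains adherence.* Sections 1.2 and 4.2 make the R33 conditional on the go/no-go criteria. A reader might infer that 9.4.3 could send a poorly attended programme into the R33, or that feasibility has no bearing on Aim 2. The documents do not support either: a failed adherence criterion stops the R33, and Sections 1.1 and 4.1 both tie duration to the criteria. This stands and limits the harm.

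*Adherence is specified outside 9.4.* Section 6.4 gives the ratio, Section 3 the threshold, Section 9.1 the hypothesis and Section 9.3 the analysis set, and comparing one mean with 75% needs no model. That is enough for a single week-16 figure. It does not cover weeks 8 and 12. The endpoint table in Section 3 leaves the number possible without a figure, so a time-point reading is conceivable, but Section 6.4 then fixes it at 96.

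*Section 9.4.3 refers to the primary endpoints, which include adherence.* The only criterion it names is a Cohen's d, which cannot be applied to a 75% threshold.

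**Conclusion.** The concern holds as an inconsistency in the duration-selection rule, together with an adherence measure that does not work before week 16. Its reach is the Aim 2 result. Section 9.4.3 can name a duration that the go rule rejects, and the 96-session denominator can reject a shorter duration at which adherence to date was at least 75%. The caps of 50% and 75% are arithmetic from Section 6.4 and rest on no assumption. The 80/75/70% path is an illustration with assumed rates.

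It is tempting to read the 3% to 10% figure, or its complement of 90% to 97%, as how often the two rules disagree. It is not. It rests on an assumed true adherence of 70% and an assumed SD of 20 to 30 points, and it shows the Section 3 gate doing its job when adherence is below threshold. Disagreement also requires the d criterion on all three tasks, and the documents give no basis for that joint probability. If true adherence were 85%, the adherence criterion would rarely fail. The point should be settled before analysis, but it does not threaten the go/no-go gate itself.

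**What to change.** Reconcile Sections 3, 4.1, 6.4 and 9.4.3 so that one selection rule is stated throughout.

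- **6.4:** define adherence at each assessment point as sessions completed out of sessions scheduled to that point: 48 at week 8, 72 at week 12 and 96 at week 16. Say that sessions scheduled after a participant stops training count as not completed, in keeping with the all-participants analysis set in Section 9.3.
- **9.4.2:** report mean adherence in all participants at weeks 8, 12 and 16. A 95% interval is optional, since the go rule uses the observed mean.
- **9.4.3:** apply the protocol's own full set of go/no-go criteria at the same time point, name the earliest that meets them, and state that the result is no go if none does. Bring the Section 3 dosing sentence into line.
- **Boundary:** use one form throughout. Section 3 accepts exactly 75%, whereas Section 9.1 speaks of exceeding it; week 12 of the illustration falls on that boundary.

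The cost is a few sentences in 6.4, 9.4.2 and 9.4.3, wording alignment in Sections 3 and 9.1, and one descriptive summary from the adherence dashboard described in 6.4. No new data are needed.
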